5.10. Efficacy Analyses

A secondary objective of the study is to document any antitumor activity. The efficacy analysis will be conducted on the intent-to-treat (ITT) population. Tumor response data will be tabulated according to assigned treatment. Best overall response will be also summarized by assigned treatment. A listing will also be provided. The objective response rate (ORR=CR+CRu+PR) and disease control rate (DCR=CR+CRu+PR+SD) along with the 95 exact confidence interval (CI) will be tabulated. For patients having CR/CRu/PR, the median duration of response, together with a 95% CI will be estimated using Kaplan-Meier method. The median PFS and OS will be estimated along with 95% CI using Kaplan-Meier method.

Any deaths observed during the study will be summarized descriptively for each patient observed to have died. See section 5.4 pertaining to missing data for additional details.

Similar efficacy analyses will be conducted for those with lung disease versus not.

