- **Olaratumab Monotherapy Treatment Period:** begins at the first administration of olaratumab 20 mg/kg on Day 1 of Cycle 1 and ends on Day 21 of Cycle 1.
- **Combination Olaratumab plus Doxorubicin Therapy Treatment Period:** begins after the post Cycle 1 treatment biopsy is obtained, with the first administration of olaratumab 20 mg/kg and doxorubicin 75 mg/m² on Day 1 of Cycle 2, followed by the administration of olaratumab 20 mg/kg on Day 8 of Cycle 2. This treatment period continues from Cycle 3 through Cycle 7 with the administration of olaratumab at a dose of 15 mg/kg on Days 1 and 8 and doxorubicin 75 mg/m² on Day 1 of each 21-day cycle. Upon completion of the combination therapy treatment period, the patient will no longer receive study treatment.
- **Post-discontinuation Follow-Up:** begins the day after the patient and the investigator agree that the patient will no longer continue study treatment.
 - **Short-term follow-up:** begins the day after the patient and the investigator agree that the patient will no longer continue study treatment and lasts approximately 30 days (±7 days). The short-term follow-up visit occurs at or near the end of the short-term follow-up period (±7 days).
 - Follow-up for safety - Patients who undergo surgical resection will be followed for safety for approximately 30 days (±7 days) after surgery.
 - **Long-term follow-up:** begins the day after short-term follow-up is completed.
 - Follow-up for progression - Patients who discontinue study treatment, or have completed 6 cycles of combination therapy, and have not progressed and have not initiated a new systemic treatment for their disease will be assessed for progression by imaging studies every 6 weeks (<7 days) until PD. Patients who have had surgical resection will not be followed for subsequent progression by imaging studies.

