10.6. Efficacy

The following secondary efficacy endpoints will be measured:

Progression-free survival (PFS): is defined as the time from enrollment until the first radiographic documentation of objective progression as defined by RECIST (v1.1) ([Attachment 8](#)), or death from any cause. Patients who die without a reported prior progression will be considered to have progressed on the day of their death. Patients who did not progress or who are lost to follow-up will be censored at the day of their last radiographic tumor assessment. If no baseline or postbaseline radiologic assessment is available, the patient will be censored at the date of enrollment. If death or PD occurs after 2 or more consecutive missing radiographic visits, censoring will occur at the date of the last radiographic visit prior to the missed visits. The use of a new anticancer therapy or the performance of a surgical resection prior to the occurrence of PD will result in censoring at the date of last radiographic assessment prior to initiation of new therapy or surgical resection.

3-month PFS: estimated as the total number of patients who did not progress 3 months after enrollment divided by the total number of patients.

Overall response rate (ORR): estimated as the total number of CRs, complete responses unconfirmed (CRus), and PRs divided by the total number of patients.

Disease control rate (DCR): is computed as the total number of patients with the best overall response of CR, CRu, PR, or SD divided by the total number of patients.

Rate of Resectability: is defined as the total number of patients who are resectable (see definition of resectability in Section 4) divided by the total number of patients.

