- **Consolidated AEs** are composite AE terms consisting of synonymous Medical Dictionary for Regulatory Activities (MedDRA) preferred terms (PTs) to allow meaningful interpretation of the AE data. Consolidated AE categories and PTs will be maintained at compound level and reported in the CSR.
- **Serious adverse event (SAE)** is any AE that results in one of the following outcomes:

- death
 - a life-threatening experience (that is, immediate risk of dying)
 - persistent or significant disability/incapacity
 - initial or prolonged in-patient hospitalization
 - congenital anomaly/birth defect
 - considered significant by the investigator for any other reason
- **Treatment-emergent adverse event (TEAE)** is defined as an event that first occurred or worsened in severity after baseline and 30 days after the last dose of study treatment and related SAEs reported beyond 30 days after the last dose of study treatment, where last dose stands for actual dose, that is, 0 dose is not counted as last dose.

Exposure-related variables are listed below:

- **Dose exposures:** As reported in the eCRF
- **Number of dose level reductions:** Sum of the number of dose level reductions as reported in the eCRF
- **Dose delays:** As reported in the eCRF
- **Dose withheld/skip (Not Administered):** As reported in the eCRF
- **Dose interruption:** As reported in the eCRF

5.3.5. *Efficacy Variables*

The study was not designed to make an efficacy assessment. However, any tumor response data will be tabulated according to assigned treatment.

Circulating tumor cells (CTC) will be assessed at pre-olaratumab and post-olaratumab in whole blood.

Secondary efficacy analysis will be performed to investigate antitumor activity by assigned treatment. Response and disease progression will be evaluated using Response Evaluation Criteria in Solid Tumors (RECIST) version 1.1 (Eisenhauer et al. 2009) for all tumors.

Overall Response Rate (ORR) is defined as the percentage of patients achieving a best overall response of either Complete Response (CR), complete responses unconfirmed (CRus) or Partial Response (PR), as determined by RECIST 1.1. The best overall response is the best response from the start of the treatment until PD/recurrence.

Disease control rate (DCR) is defined as the percentage of patients achieving a best overall response of CR, CRu, PR, or SD as determined by RECIST 1.1. Patients who do not have any

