postbaseline tumor response assessments for any reason are considered non-responders and are included in the denominator when calculating the response rate.

Progression-free survival (PFS) is defined as the time from the date of first study dose to the first date of radiologic disease progression or death due to any cause. [Table JGDM.5.1](#) defines the rules of censoring to be applied to PFS.

3-month Progression-free survival (PFS) is defined as the 3-month PFS rate as estimated using Kaplan-Meier methods. PFS is as defined above.

Rate of Resection is defined to be the percentage of patients whose tumors are determined to be resectable divided by the total number of patients. The evaluation of resectability of a tumor is determined by the surgeon in consultation with the multi-disciplinary team, and depends on the tumor stage and the patient's co-morbidity. The primary aim of surgery is to completely excise the tumor with a margin of normal tissue.

Table JGDM.5.1. Censoring Rule of PFS Primary Analysis

Situation	Event / Censor ^d	Date of Event or Censor ^e
Tumor progression^a or death	Event	Earliest date of PD or death
No tumor progression and no death	Censored	Date of last adequate radiological assessment or date of first study dose
unless		
No baseline radiological tumor assessment available	Censored	Date of first study dose
No adequate^b postbaseline radiological tumor assessment available and death reported after 2 scan intervals ^c following first study dose	Censored	Date of first study dose
New anticancer treatment (including surgery) started and no tumor progression or death within 14 days	Censored	Date of adequate radiological assessment prior to (start of new therapy +14 days) or date of first study dose (whichever is later)
Tumor progression or death documented immediately after 2 or more consecutive missing scan intervals following last adequate radiological tumor assessment or first study dose (whichever is later)	Censored	Date of last adequate radiological assessment prior to the missing assessment or date of first study dose

Abbreviations: CR = complete response; PD = progressive disease; PFS = progression free survival; PR = partial response; SD = stable disease.

- a Symptomatic deteriorations (that is, symptomatic progressions, which are not radiologically confirmed) will not be considered as disease progressions.

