A listing of SAEs will be produced.

The following death reports will be provided:

- summary of deaths (all deaths and deaths within 30 days of last dose of study drug)

The following AE of special interest (AESIs) summary will be provided:

- summary of treatment-emergent AESIs by AESI group and PT (regardless of causality and study drug-related)
- listing of treatment-emergent AESIs

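### SAP 5.10 plans a Kaplan-Meier median OS with 95% CI, but OS is neither a named objective nor a defined variable, and survival is not systematically followed after progression, new systemic treatment or resection

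*SAP*

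**What the plan says.** SAP 5.10 (Efficacy Analyses) states: "The median PFS and OS will be estimated along with 95% CI using Kaplan-Meier method". The same section then adds: "Similar efficacy analyses will be conducted for those with lung disease versus not". It does not say whether that includes OS.

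The only time-to-event variable defined in SAP 5.3.5 with a start date, an event and censoring rules is PFS. Its table is titled "Censoring Rule of PFS Primary Analysis", and there is no counterpart for OS. The secondary objectives (Protocol 5.2.2, SAP 4.2) and the endpoints in Protocol 10.6 list PFS, 3-month PFS, ORR, DCR and resectability, but not OS.

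On follow-up, Protocol 6.2 says the short-term period "begins the day after the patient and the investigator agree that the patient will no longer continue study treatment and lasts approximately 30 days". Of surgery it says: "Patients who undergo surgical resection will be followed for safety for approximately 30 days". Long-term follow-up is imaging every 6 weeks until PD, for patients who have neither progressed nor started a new systemic treatment. Resected patients are not imaged for later progression.

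Some deaths are captured. Protocol 10.6 counts death without prior progression as a PFS event: "Patients who die without a reported prior progression will be considered to have progressed on the day of their death". SAP 5.10 describes deaths observed on study, and SAP 5.11.2 tabulates deaths overall and those up to 30 days after the final dose.

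**The concern.** A Kaplan-Meier median needs a defined time origin and event, and censoring that carries no information about the patient's remaining survival. The plan supplies none of these for OS. The programmer would have to choose the origin and the censoring date once data exist. More importantly, the protocol stops looking for deaths at, or shortly after, progression or resection. Progression plausibly marks worse survival and resectability better survival, so the censored patients do not resemble those who remain at risk.

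The clinical study report could then carry an OS median and interval that readers cannot interpret. If the median is not reached, that could mean long survival, or only that contact ended. If the lung-disease analyses include OS, the same problem recurs in smaller groups.

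**Working it through.** **1. Is there a plan figure to reproduce?** Not for OS: no OS event count, sample size or follow-up length is stated. The only sample-size figure, the 95% CI for 17/35, reproduces as an exact binomial interval (31.4% to 66.0%, against the stated 31% to 66%), but it concerns the PDGFRα hit rate.

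**2. When does observation for death end?**

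| Route out | Scheduled observation | Source |
|---|---|---|
| Stops for PD | 30-day visit only | Protocol 6.2, Attachment 1 |
| Resection | about 30 days of safety follow-up | Protocol 6.2, Attachment 1 |
| Stops, or completes 6 combination cycles, without PD or resection | every 6 weeks until PD | Protocol 6.2, Attachment 1 |
| Starts new systemic treatment | drops out of imaging follow-up | Protocol 6.2 |

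The post-treatment schedule in Attachment 1 has no survival-status row. Its long-term column holds only imaging, toxicity and patient disposition. Under Protocol 8.1.2.1, deaths from progression are not reported as SAEs unless possibly drug-related. Study completion (6.2.1) and the second database lock (10.1) depend on patients completing or discontinuing, by progression or resection, and finishing follow-up. Neither depends on deaths.

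**3. How long is that?** Maximum treatment is 7 × 21 = 147 days. A patient who progresses or is resected by the end of Cycle 7 is scheduled for at most about 147 + 30 = 177 days, or 177/30.4375 = 5.8 months (6.0 months with the +7-day window), ignoring dose delays. The protocol's only reference OS medians (section 5.1, prior Phase 2 study) are 26.5 and 14.7 months.

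**4. Illustration.** Inputs:
- Median PFS 6.6 and median OS 26.5 months (Protocol 5.1, advanced disease, not this population).
- A share f = 5%, 10% or 20% of PFS events are deaths (assumed; no source in the documents).
- 0% or 60% of patients are resected at 2 to 5.5 months while event-free, at random and with OS unchanged (assumed).
- Exponential PFS, with exponential post-PD survival tuned to give median OS 26.5 months.
- Observation ends at PD or 1 month after it, or 1 month after resection.
- 35 patients, 4,000 simulated trials per row, censoring at last contact.

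Hand check: with no resection and observation ending at PD, only deaths that are themselves PFS events are seen, so expected deaths = f × 35 = 1.75, 3.5 and 7.0. With 60% resected, 0.4 × 35 = 14 patients reach a PFS event unresected, giving f × 14 = 0.7, 1.4 and 2.8, plus a few deaths in the month after resection. The simulated values agree:

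| Resected | Observation after PD | Mean observed deaths (f = 5/10/20%) | OS median not reached |
|---|---|---|---|
| 0% | 1 month | 3.0 / 4.7 / 7.9 | 81 / 70 / 41% |
| 0% | none | 1.7 / 3.45 / 7.0 | 90 / 78 / 44% |
| 60% | 1 month | 1.4 / 2.1 / 3.6 | 87 / 81 / 68% |
| 60% | none | 0.84 / 1.65 / 3.28 | 92 / 85 / 69% |

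For comparison, full survival follow-up would show 35/2 = 17.5 deaths by 26.5 months. Under the plan, a mean of only 0.3 to 2.4 patients is still at risk then.

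**The case against.** The SAP limits its own claims. It calls the analyses descriptive (5.2) and says: "The study was not designed to make an efficacy assessment". No decision uses OS, and a sparse median in a 35-patient Phase 1b report will mislead few readers. That stands, and it is why the point is minor.

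OS could also be read into the exploratory objective on clinical outcomes, or into SAP 5.2's allowance for further exploratory analyses. But neither names OS, and neither supplies follow-up.

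The illustration is soft. The share of PFS events that are deaths has no source and drives the result, and the medians come from advanced disease. Resection is simulated as unrelated to prognosis, so the figures do not demonstrate informative censoring by resection; that part is reasoned from the design. The textual finding needs none of these figures.

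One could define OS in the SAP, report follow-up and state the limitation. That would make the estimate transparent, but observation would still end at PD or resection. The simulation already censors at last contact.

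A reader might infer more than the documents support:
- *Nobody is followed past 30 days after stopping treatment.* Not so: patients who stop without PD or resection are followed until PD.
- *The final lock needs only the 30-day visit.* Protocol 10.1 also requires every patient to have completed or discontinued the study.
- *Deaths are not captured.* Deaths before PD are PFS events, and observed deaths are summarised.
- *The OS estimate would be biased in a known direction.* The documents give no death or resection rates from which to tell.

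**Conclusion.** Wrong as written; minor. Followed exactly, SAP 5.10 yields a median for an undefined variable, from a curve censored at or soon after PD or resection. Independent censoring is not credible there, and a median that is not reached would be uninterpretable. This rests on the objectives, the variable definitions and the follow-up schedule.

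The size is illustrative only: about 1 to 8 observed deaths among 35 patients, and no OS median in about 41% to 92% of simulated trials, under the stated assumptions. No named objective or trial decision is affected.

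**What to change.** Delete 'and OS' from the sentence in SAP 5.10, and keep the descriptive death summaries in 5.10 and 5.11.2. This also keeps OS out of the lung-disease analyses. If a reason is wanted, add: *OS is not estimated because survival status is not systematically followed after disease progression, after the start of new systemic treatment, or beyond the approximately 30-day safety follow-up after resection.*

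If the sponsor wants OS, an SAP edit alone is not enough. It needs survival follow-up by protocol amendment, plus an OS definition and censoring rule in the SAP.

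The deletion costs one phrase and, optionally, one added sentence. The downside is that the report carries no OS figure.

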5.11. Safety Analyses

All the safety analyses will be performed based on Safety Population. Most safety analyses will be conducted on entire treatment phase. However, a selection of safety analyses will be conducted on cycle 1 only and cycle 2 onward separately. See section 5.4 pertaining to missing data for additional details.

5.11.1. Study Drug Exposure

Study drug exposure will be summarized based on Safety Population. The summary will include duration of treatment, number of infusions, the number of cycles received per patient, cumulative dose, cumulative dose level, weekly dose intensity, relative dose intensity, by assigned treatment. Details of study drug administration will be included in patient listings.

Dose modifications, delays and discontinuations will also be summarized.

The exposure formulas are defined below.

Olaratumab:

- Duration of treatment (weeks) = $([\text{Date of last dose} - \text{date of first dose}] + 21) \div 7$
- Cumulative dose (mg) = Sum of all doses
- Calculated dose level administered (mg/kg) = $\frac{\text{Actual total dose of olaratumab (mg)}}{\text{Closest body weight prior to that administration (kg)}}$
Cumulative dose level (mg/kg) = Sum of all calculated infusion doses
- Dose intensity (mg/kg/week) = $(\text{Cumulative dose level}) \div (\text{Duration of treatment})$
- Planned dose intensity (mg/kg/week)
 - Cycle 1 = 20 mg/kg/three weeks
 - Cycle 2 = 20 mg/kg/three weeks
 - Cycle 3-7 = 15mg/kg/three weeks

- Relative dose intensity (%) (Based on planned dose)= (Dose intensity) ÷ (Planned dose intensity) x 100

Doxorubicin:

- Duration of treatment (weeks) = ([Date of last dose – date of first dose] + 21) ÷ 7
- Cumulative dose (mg) = Sum of all doses
- Cumulative dose level (mg/m²) = Sum of (dose administered at each infusion [mg] ÷ Last available body surface area [BSA] [m²] prior to that infusion)
- BSA (m²) = 0.007184 * weight (kg) ^0.425 * height (cm) ^0.725
- Dose intensity (mg/m²/weeks) =(Cumulative dose level) ÷ (Duration of treatment)
- Planned dose intensity (mg/m²/week) = 75 mg/m²/ 3 weeks= 25 (Cycle 2-7)
- Relative dose intensity (%)=(Dose intensity) ÷ (Dose intensity) x 100

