6.2. Summary of Study Design

Study JGDM is an open-label, single-arm, multicenter, multicountry Phase 1b study to enumerate whole blood CTCs and to characterize PDGFR α and PDGFR β and canonical ligands (*PDGF-A, B, C* and *D*) expression changes pre- and post-olaratumab monotherapy in tumor tissue in patients with potentially resectable STS.

Patients are to be treated with 20 mg/kg of olaratumab on Day 1 and Day 8 of Cycle 1, followed by up to 6 cycles (Cycle 2 – Cycle 7) of combination therapy with olaratumab plus doxorubicin. For Cycle 2, olaratumab is to be dosed at 20 mg/kg on Day 1 and Day 8 and doxorubicin is to be dosed at 75 mg/m² on Day 1. For Cycle 3 – Cycle 7, olaratumab is to be dosed at 15 mg/kg on Day 1 and Day 8 and doxorubicin is to be dosed at 75 mg/m² on Day 1. Each cycle of treatment is defined as an interval of 21 days. Approximately 35 patients are to be enrolled.

Starting with the first cycle of combination therapy (Cycle 2), the use of dexrazoxane (in a 10:1 ratio vs. doxorubicin dose) to mitigate cardiotoxicity during treatment with doxorubicin is allowed at the investigator's discretion and is recommended for all patients receiving 5 or more cycles of doxorubicin.

[figure not shown]
Tissue biopsies are required pre- and posttreatment with olaratumab monotherapy. The pretreatment tissue biopsy is to be performed within the screening period. The posttreatment tissue biopsy is to be performed after completion of the lead-in cycle of olaratumab monotherapy and prior to the initiation of combination therapy in Cycle 2. An optional third tissue biopsy (or tissue from a posttherapy surgical resection specimen) may be performed at the end of the patient's study treatment. If clinically feasible, the tissue biopsies should be taken from the same primary tumor lesion. If the patient has an additional surgical resection, tissue from this procedure is requested. Refer to Section 8.2.3.2 for details on tissue biopsies.

Whole blood samples for CTC analyses are to be collected predose at Cycle 1 Day 1 (C1D1), at Cycle 1 Day 8 (C1D8), at Cycle 2 Day 1 (C2D1), at Cycle 2 Day 8 (C2D8), at Cycle 3 Day 1 (C3D1), and at the end of the patient's study treatment or at the time of surgical resection. Refer to Section 8.2.3.1 for details on blood samples.

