7.2.1. Treatments Administered

Table JGDM.1 shows the treatment regimens to be administered in this study.

Table JGDM.1. Treatment Regimens

Treatment	Cycle Length (Days)	Study Drug	Dose	Timing	Route
Monotherapy Cycle 1	21	Olaratumab ^a	20 mg/kg	approximately 1 hour infusion D1, D8	IV
		1-hour (\pm 5 minutes) Observation Period ^b			
Combination Therapy Cycle 2	21	Olaratumab ^a	20 mg/kg	approximately 1 hour infusion D1, D8	IV
		1-hour (\pm 5 minutes) Observation Period ^b followed by			
		Doxorubicin ^c	75 mg/m ²	IV injection on D1	IV
Combination Therapy Cycle 3 – Cycle 7	21	Olaratumab ^a	15 mg/kg	approximately 1 hour infusion D1, D8	IV
		Doxorubicin ^c	75 mg/m ²	IV injection on D1	IV

Abbreviations: D = day; eCRF = electronic case report form; IRR = infusion-related reaction; IV = intravenous; PO = orally.

- ^a Premedicate all patients with the following (or equivalent) medications: a histamine H1 antagonist (for example, diphenhydramine) and dexamethasone intravenously 30–60 minutes prior to the olaratumab doses on Days 1 and 8 of Cycle 1. For subsequent cycles, premedicate all patients with a histamine H1 antagonist (for example, diphenhydramine) intravenously 30–60 minutes prior to each dose of olaratumab. Additional premedication may be provided at the investigator's discretion. Premedication **must be** provided in the setting of a prior Grade 1-2 IRR, as detailed in Section 7.2.2 and Section 7.2.3.1.1.1. All premedication administered must be adequately documented in the eCRF.
- ^b A 1-hour (+5 minutes) Observation Period is required after the administration of the initial 2 cycles of olaratumab. During the Observation Period, collect vital signs 3 times: 1) within 15 minutes (+5 minutes) prior to olaratumab infusion, 2) within 1 hour (+5 minutes) after completion of the olaratumab infusion, and 3) within 1 hour (+5 minutes) after completion of the doxorubicin infusion. If no evidence of an IRR manifests during the initial 2 cycles of olaratumab, then no observation period is required for subsequent treatment cycles. In the event an IRR occurs thereafter, then the 1-hour Observation Period should be reinstated; see Section 7.1.2. Thereafter (Cycles 3+), obtain vital signs 2 times: 1) within 15 minutes (+5 minutes) prior to olaratumab infusion and 2) within 1 hour (+5 minutes) after completion of the doxorubicin infusion.

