5.1. Study Design and Sample Size Consideration

Study JGDM is an open-label, single-arm, multicenter, multicountry Phase 1b study to enumerate whole blood CTCs and to characterize PDGFR α and PDGFR β and canonical ligands (*PDGF-A, B, C* and *D*) expression changes pre- and post-olatumab monotherapy in tumor tissue in patients with potentially resectable STS.

Patients are to be treated with 20 mg/kg of olatumab on Day 1 and Day 8 of Cycle 1, followed by up to 6 cycles (Cycle 2 – Cycle 7) of combination therapy with olatumab plus doxorubicin. For Cycle 2, olatumab is to be dosed at 20 mg/kg on Day 1 and Day 8 and doxorubicin is to be dosed at 75 mg/m² on Day 1. For Cycle 3 – Cycle 7, olatumab is to be dosed at 15 mg/kg on Day 1 and Day 8 and doxorubicin is to be dosed at 75 mg/m² on Day 1. Each cycle of treatment is defined as an interval of 21 days. Approximately 35 patients are to be enrolled.

Starting with the first cycle of combination therapy (Cycle 2), the use of dexrazoxane (in a 10:1 ratio vs. doxorubicin dose) to mitigate cardiotoxicity during treatment with doxorubicin is allowed at the investigator's discretion and is recommended for all patients receiving 5 or more cycles of doxorubicin.

Tissue biopsies are required pre- and posttreatment with olatumab monotherapy. The pretreatment tissue biopsy is to be performed within the screening period. The posttreatment tissue biopsy is to be performed after completion of the lead-in cycle of olatumab monotherapy and prior to the initiation of combination therapy in Cycle 2. An optional third tissue biopsy (or tissue from a posttherapy surgical resection specimen) may be performed at the end of the patient's study treatment. If clinically feasible, the tissue biopsies should be taken from the same primary tumor lesion. If the patient has an additional surgical resection, tissue from this procedure is requested. Refer to Protocol Section 8.2.3.2 for details on tissue biopsies.

Whole blood samples for CTC analyses are to be collected predose at Cycle 1 Day 1 (C1D1), at Cycle 1 Day 8 (C1D8), at Cycle 2 Day 1 (C2D1), at Cycle 2 Day 8 (C2D8), at Cycle 3 Day 1 (C3D1), and at the end of the patient's study treatment or at the time of surgical resection. Refer to Protocol Section 8.2.3.1 for details on blood samples.

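### The SAP's olaratumab treatment duration adds 21 days after the last infusion, so a patient whose last infusion is an on-schedule Day 8 dose is credited with one extra week in total

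*SAP*

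**What the plan says.** The olaratumab list in SAP 5.11.1 gives "Duration of treatment (weeks) = $([\text{Date of last dose} - \text{date of first dose}] + 21) \div 7". The doxorubicin list in the same section repeats the formula. The olaratumab result is then used as a divisor: "Dose intensity (mg/kg/week) = $(\text{Cumulative dose level}) \div (\text{Duration of treatment", which in turn feeds relative dose intensity.

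The schedule is stated consistently. SAP 5.1: "Each cycle of treatment is defined as an interval of 21 days". Table JGDM.1 (Protocol 7.2.1) lists olaratumab as "approximately 1 hour infusion D1, D8" in every cycle and doxorubicin on Day 1 only. Protocol 6.2 gives the doses: "Patients are to be treated with 20 mg/kg of olaratumab on Day 1 and Day 8 of Cycle 1"; "For Cycle 2, olaratumab is to be dosed at 20 mg/kg on Day 1 and Day 8"; and for Cycles 3 to 7, "olaratumab is to be dosed at 15 mg/kg on Day 1 and Day 8". The same section says that the monotherapy period "begins at the first administration of olaratumab 20 mg/kg on Day 1 of Cycle 1 and ends on Day 21 of Cycle 1".

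Neither document defines the date of last dose as Day 1 of the last cycle, or gives a reason for counting 21 days after a Day 8 infusion. Where the SAP does explain last dose, in the definition of treatment-emergent events (SAP 5.3.4), it means the last dose actually given.

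**The concern.** The tail added after the last dose should bring the count to the end of the last cycle. A fixed 21 days does this for a drug given once, on Day 1. For a drug also given on Day 8, it runs a week past the end of the cycle.

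Three planned outputs depend on this: duration of treatment, weekly dose intensity and relative dose intensity. The rule also measures patients on different clocks, because whether the final Day 8 dose was given changes the reported length of treatment. Protocol 7.2.3.1 allows a Day 8 dose to be skipped, and Protocol 6.2 foresees stopping early for progression, toxicity or resection, so both situations can be expected. As a proportion of duration, the excess is largest in short courses.

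**Working it through.** **Inputs.** Cycle length 21 days (SAP 5.1). Olaratumab on Days 1 and 8, at 20 mg/kg per infusion in Cycles 1–2 and 15 mg/kg in Cycles 3–7 (Protocol 6.2). Doxorubicin 75 mg/m² on Day 1 of Cycles 2–7. Dosing is taken as exactly on schedule unless stated.

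**1. Reproduce the plan's own figure.** The section evaluates one result, a planned doxorubicin intensity of 25 mg/m²/week. For c cycles of doxorubicin, duration = (21(c − 1) + 21)/7 = 3c weeks, and 75c/3c = 25. The +21 rule is therefore right for doxorubicin.

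**2. Olaratumab, last infusion on Day 8 of cycle c.** Last minus first dose = 21(c − 1) + 7 days. SAP duration = (21(c − 1) + 7 + 21)/7 = 3c + 1 weeks, against 3c weeks of treatment cycles.

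**3. Cross-check on Cycle 1.** The monotherapy period runs from Day 1 to Day 21. The general duration rule in SAP 5.3 (end minus start plus 1, divided by 7) gives (20 + 1)/7 = 3 weeks. The exposure formula gives (7 + 21)/7 = 4.

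**4. Effect on dose intensity.** Cumulative dose level is 2 × 20 = 40 mg/kg after one cycle, 80 after two, and 80 + 5 × 30 = 230 after seven.

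| Cycles | SAP weeks | Cycle weeks | SAP intensity (mg/kg/week) | Intensity over cycle weeks (mg/kg/week) | Understated by |
|---|---|---|---|---|---|
| 1 | 4 | 3 | 40/4 = 10.0 | 40/3 = 13.33 | 25% |
| 2 | 7 | 6 | 80/7 = 11.43 | 80/6 = 13.33 | 14% |
| 7 | 22 | 21 | 230/22 = 10.45 | 230/21 = 10.95 | 4.5% |

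The understatement is 1/(3c + 1). The excess in duration is 1/(3c): 33% after one cycle and 4.8% after seven.

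**5. Last infusion on Day 1.** (21(c − 1) + 21)/7 = 3c weeks, so there is no excess. After one cycle, a patient who missed Day 8 shows 20/3 = 6.67 mg/kg/week and a fully dosed patient shows 10.0. Half the dose is reported as 67% of the intensity.

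**6. Day 8 shifted.** Attachment 1 allows ±3 days within a cycle, and Protocol 7.2.3.1 allows a Day 8 delay of up to 7 days. With the last Day 8 dose moved by −3, +3 or +7 days, the excess over the 21-day cycle is 4, 10 or 14 days.

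**7. Against the printed planned intensity.** SAP 5.11.1 prints 20 mg/kg per three weeks for Cycles 1 and 2, and 15 for Cycles 3–7. Averaging these over the cycles received (an assumption, since the SAP does not say how to combine them) gives 20/3 = 6.67 mg/kg/week for one or two cycles and (2 × 20 + 5 × 15)/21 = 5.48 for seven. A fully dosed patient then shows 10.0/6.67 = 150%, 11.43/6.67 = 171% and 10.45/5.48 = 191%. With duration alone corrected, all three become 200%.

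**The case against.** The strongest reply is that nothing important depends on this formula. The trial is single-arm and its analyses are mainly descriptive. The same section also reports infusions, cycles, cumulative dose and administration listings, and SAP 5.8 adds omissions, reductions and delays, so true exposure can be recovered. No primary biomarker, efficacy or stopping result uses the formula. All of this stands, and it limits the weight of the point.

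One could also defend a flat 21-day tail as a deliberate convention. The SAP does not present it as one. It also uses the result as the divisor of a weekly rate, where a tail beyond the cycle biases the rate downwards.

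A reader might infer that fully dosed patients would be reported as dosed less intensively than planned. The SAP as printed does not support that: against its own planned figures they show 150% to 191%. The shortfall (75%, 85.7% and 95.5% for one, two and seven cycles) appears only against a plan that counts both infusions, which is not what the SAP prints for planned intensity.

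A reader might also take the excess as one week per cycle, or as affecting every patient. It is one fixed week per patient with on-schedule Day 8 dosing, and it is absent when the last infusion falls on Day 1. The 33% figure belongs only to patients who stop after one cycle having received Day 8, and the documents give no number of such patients.

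**Conclusion.** The formula is wrong as written for olaratumab. For a patient whose last infusion is an on-schedule Day 8 dose, it overstates duration by exactly one week. If all doses were given on schedule, actual dose intensity is understated by 25%, 14% and 4.5% after one, two and seven cycles. The result rests on the 21-day cycle, the Day 1 and Day 8 schedule, and reading last dose as the dose actually given.

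The consequence is confined to descriptive exposure summaries. It matters most for short courses and for any exposure table restricted to Cycle 1. SAP 5.11 splits a selection of safety analyses into Cycle 1 and Cycle 2 onward without saying whether exposure is among them. If it is, a full on-schedule course would show 4 + 19 = 23 weeks by period and 22 overall, for 21 weeks of cycles.

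This is a correction that should be made, not a threat to the trial's conclusions.

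**What to change.** For olaratumab, define duration (weeks) as ([Day 1 date of the last cycle in which olaratumab was given − date of first dose] + 21)/7. Leave the doxorubicin duration formula unchanged.

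Do not instead add 14 days after a Day 8 infusion. The two rules agree only when Day 8 is on schedule. In a one-cycle patient with the Day 8 dose given on Day 15, the Day 1 rule gives 21/7 = 3 weeks, while adding 14 days gives (14 + 14)/7 = 4 and brings the extra week back.

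Make the change together with reconciling the planned olaratumab intensity lines in SAP 5.11.1, which count one infusion per three weeks, with the two-infusion schedule in Protocol 6.2 and SAP 5.1. The duration error partly masks that discrepancy, and correcting duration alone moves printed relative dose intensity for a fully dosed patient to 200%.

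The cost of the duration change is one line of SAP wording and a small programming change, using dosing dates and cycle labels already collected.
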